### **A. SPECIFIC AIMS**

**Objectives:** Study objectives are consistent with VA housing recommendations focusing on patient recovery, health services promotion, and treatment implementation evaluation. GMI will be compared to a control treatment condition (CT) on (**Specific Aim I; Five outcomes:** (Primary H1): treatment engagement; (Primary H1): substance use; (Secondary H2): psychosocial integration (e.g., social support, community participation); (Secondary H3) quality of life/psychiatric indices; and (Secondary H4): number of days engaging in structured/productive work activities in the 6-month follow up. **Specific Aim II** involves a process evaluation for documenting (A) formative (e.g., developmental), (B) process, and (C) summative outcomes; and **Specific Aim III** involves estimation of cost of intervention in terms of direct costs, indirect costs of staff, costs of capital and workload measures for future implementation and dissemination research.

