## **C12. Overview of the statistical analysis plan.**

**Effectiveness analyses:** all health services and participant outcomes (see section C9) will be obtained at three time points (month 1, 3 and 6-months post-randomization). These variables include: (a) Substance use outcomes (e.g., standard drinks/day (SEC), peak standard drinks/day, # drinking days, # binge drinking days, # illicit drug use days, etc.); (b) Treatment engagement (e.g. # of substance abuse/mental health treatment sessions attended, # AA sessions attended, # AA sponsor contacts; (c) Psychosocial adjustment (social support, community participation) and (d) Quality of life/psychiatric indices (QOLS, SF-12, BSI-18); (e) Engagement in structured/productive work activities (% of days each month engaged in work or volunteer activities); (c) Process measures (CPOSS-VA, HAQ) will be assessed at 1-month follow up.

**Analysis sets.** The ITT sample comprises all randomized participants. The per-protocol/completer sample comprises participants who are compliant with protocol requirements and for whom all required measurements have been made. Primary analyses will be carried out using the ITT analysis set.

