sensitivity analysis will be made to balance between model complexity and reduction in bias. We will use Poisson distribution with a log-link for count outcomes (e.g., # drinking/drug use days, # days SUD treatment, # days structured work activities), Binomial distribution with logit-link for binary outcomes (e.g. attended treatment/did not attend treatment) and Gaussian distribution with identity-link for continuous outcomes (e.g., standard drinks). When we suspect over-dispersion in the count models that is beyond what is assumed by the Poisson GLMM then we will use Negative Binomial distribution. To deal with zero inflation, we will use zero-inflated Poisson (ZIP) and negative binomial (ZINB) models. For multiple outcomes, we will use a joint model based on linking the GLMM models for each outcome type by assuming a joint statistical distribution for the random coefficients (intercept and slopes). Let  $Y_{ijk}$  be the response from the  $k$ th outcome for subject  $i$  at occasion or time  $j$  ( $i=1, \dots, n$ ;  $k=1, \dots, K$ ;  $j=1, 2, \dots, n_i$ ). The GLMM can be given as,  $E(Y_{ijk} | X_{ij}(t), Z_{ij}) = g^{-1}(X_{ij}(t)\beta_k + Z_i b_{ik})$ , where  $b_{ik} \sim N(0, G_k)$  and  $X_i$  and  $Z_i$  represent vectors of fixed and random effect covariates, respectively, and  $G_k$  is the covariance matrix for  $b_{ik}$ . We will use a random coefficient model with shared random intercept and random slope for each outcome. The resulting 'over all' covariance matrix (D) from this model will provide standard error estimates that account for correlation among the multiple outcomes. A key assumption for these models is conditional independence where the responses are independent given the random effects. These models can be fitted using Proc NLMIXED or GLIMMIX in SAS v9.3.

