**C12d. Analysis plan for Clinical, Social, and Quality of Life outcomes (Specific AIM I; Hypotheses 1 through 4):** To evaluate the relative efficacy of (a) GMI and (b) CT on (a) five health services outcomes (i) substance use (ii) treatment engagement, (iii) psychosocial integration (e.g., social support, community participation), (iv) quality of life/psychiatric indices, and (v) # of days engaging in structured/productive work activities. The longitudinal trajectory of efficacy outcomes will be compared using the GLMM approach, which accommodates missing at random (MAR) data and a wide range of data types/distributional assumptions: counts (e.g., # AA sessions, # times talking with AA sponsor, # substance abuse treatment sessions attended); dichotomous (e.g., abstinent/not abstinent), proportions (proportion days not drinking alcohol or using illegal drugs), and ordinal (e.g. CPOSS-VA, QOLS). When the number of zeroes is in excess of what is normally expected from a poisson model, we will fit GLMM to accommodate zero-inflation. We will use negative binomial regression to deal with over dispersion. Logit link for dichotomous outcomes, log link for count outcomes will be considered. The basic modeling procedure involves using the longitudinal outcome measurements within each of the domains separately as the dependent (outcome) variable, with intervention group (fixed effect), time (random effect), and time by intervention as the primary independent variables. In further multivariable modeling, additional covariables (as appropriate for a given dependent variable) will be added to the basic model to adjust for potential confounding effect of these variables. GLMM accommodates both fixed and time-varying covariates. For example, for the treatment engagement variable, the # of AA sessions measured monthly for 6 months will be an outcome variable, intervention group (GMI, CT), time, and time X intervention will be the primary independent variables in the basic (unadjusted) model, and psychiatric comorbidity (number and severity), age, race, and gender will be added in the subsequent (adjusted) model to adjust for the possible confounding effect of these variables. Unadjusted and covariate-adjusted least squares means for each outcome variable will be compared at the primary time point (month 1) and at intermediate secondary time points (months 3 and 6) using appropriate model contrasts and the Tukey-Kramer adjustment for multiple comparisons for the secondary time points. These contrast comparisons, along with corresponding 95% CI, will provide estimates of the difference in outcome means (effect sizes) for the hypothesized comparisons. For longitudinal dichotomous outcomes (e.g., maintenance of sobriety), we will compare unadjusted and covariate-adjusted proportions across the longitudinal trajectory (at 1, 3 and 6 months) for GMI and CT. For the end-of-active treatment time point, this analysis is equivalent to a logistic regression analysis.

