#### **6. Data Monitoring and Safety Plan**

Data Management and Analysis: A data analysis plan is outlined in the Data Analysis section. Briefly, the primary outcomes are (Hypothesis 1): Substance use (e.g. standard drinks, peak standard drink day, # drinking days, drinks per drinking day, binge drinking days, # illicit drug use days, etc); and (b) Treatment engagement (e.g. number of substance abuse/mental health treatment sessions attended, # AA sessions attended, # AA sponsor contacts).

Secondary outcome measures will be: (c) Psychosocial adjustment (Hypothesis 2; social support, community participation); (d) Quality of life/psychiatric indices (Hypothesis 3; QOLS, SF-12, BSI-18); (e) Engagement in structured/productive work activities (Hypothesis 4; percent of days each month engaged in work or volunteer activities); and (c) Process measures (CPOSS, HAQ) will be assessed at post-treatment (1-month follow up).

The longitudinal trajectory of efficacy outcomes will be compared using the generalized linear mixed models (GLMM) approach. GLMM accommodates missing at random (MAR) data and a wide range of data types/distributional assumptions: counts (e.g., # AA sessions, # times talking with AA sponsor, # substance abuse treatment sessions attended); dichotomous (e.g., abstinent/not abstinent), proportions (proportion days not drinking alcohol or using illegal drugs), ordinal (e.g. CPOSS-VA, QOLS). When the number of zeroes is in excess of what is normally expected from a poisson model, we will fit GLMM that can accommodate zero-inflation. We will use negative binomial regression to deal with over dispersion. Unadjusted and least squares adjusted means from the GLMM contrast comparisons, along with corresponding 95% CI, will provide estimates of the difference in outcome means (effect sizes) for the hypothesized comparisons. For longitudinal dichotomous outcomes (e.g., maintenance of sobriety), we will compare unadjusted and covariate-adjusted proportions across the longitudinal trajectory (at 1, 3 and 6 months) for the intervention groups using GLMM for a binary outcome. For the end-of-active treatment time point, this analysis is equivalent to a logistic regression analysis.

Quality Assurance: Data quality will be monitored by random inspection of the completed forms by research staff and any irregularities or problems detected will be discussed with the PI. Therapists will receive standardized

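### H4 is stated as work days over the 6-month follow-up, but the contrast labelled primary is at month 1 and no stated contrast estimates the six-month quantity

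*Combined protocol and SAP*

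**What the plan says.** The outcome behind H4 appears in five places in the combined protocol and SAP:

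- **A. Specific Aims:** "number of days engaging in structured/productive work activities in the 6-month follow up". No other Aim I outcome is given its own window there.
- **C12, effectiveness analyses:** "Engagement in structured/productive work activities (% of days each month engaged in work or volunteer activities".
- **Section 6, Data Monitoring and Safety Plan:** "percent of days each month engaged in work or volunteer activities", with H4 named.
- **C12c:** "We will use Poisson distribution with a log-link for count outcomes (e.g., # drinking/drug use days, # days SUD treatment, # days structured work activities". Negative binomial and zero-inflated versions are allowed. No offset for days observed is mentioned.
- **C12d, whose heading covers Hypotheses 1 through 4:** a number of days with no window.

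On timing, C12d says "least squares means for each outcome variable will be compared at the primary time point (month 1", and months 3 and 6 are secondary with a Tukey-Kramer adjustment. H4 is not exempted. C12d also plans a GLMM comparison of the longitudinal trajectory, with group, time and time by group as the main terms. The Productive Work Activities Calendar (PWAC) is given at baseline and months 1, 3 and 6 (Table 4). Its look-back period is not stated.

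**The concern.** A day count over six months, a percentage for each month and a difference at month 1 are three different quantities. H4 names the first. The only time point labelled primary gives the third. An analyst who follows C12d literally reports, as the leading H4 result, whether the groups differ at the first follow-up visit.

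The protocol's own calendar shows the gap. C1 places the sessions in week 2 and the month-1 visit in week 4 of 24. The booster session comes two months after the intervention (C7), so the month-1 contrast is taken before it.

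At stake is the interpretation of one numbered secondary hypothesis. The month-1 and six-month results could point to different conclusions, and the plan does not say which one answers H4. Several defensible H4 results would be available, and the choice among them could be made after the data are seen.

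**Working it through.** **1. Definitions side by side.**

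| Place | Unit | Window |
|---|---|---|
| Specific Aims | days | 6-month follow-up |
| C12; Section 6 | percent of days | each month |
| C12c | days, Poisson count, no stated offset | none stated |
| C12d, outcome list | days | none stated |
| C12d, primary contrast | model mean | month 1 |

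Days and percent convert into each other only when the number of days observed is known. With up to 30% loss to follow-up allowed for (C3), that number will vary, so a count model needs it as an offset. Conversion does not reconcile the windows: month 1 is 4/24 = 17% of six months on the nominal calendar.

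**2. Does another planned term estimate six-month days?** The time-by-group term asks whether the group difference changes over time. If only post-baseline visits are modelled, a benefit that is constant on the link scale makes this term zero. The group term, with the interaction in the model, depends on how time is coded. The month-3 and month-6 contrasts are visit-specific. None of these is a total or average over follow-up, although one could be formed from the same model.

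**3. The plan's own figures.** C11 gives no power for H4. Its sample size, set for substance use, reproduces: 65/0.70 = 92.9, so 93 per arm and 186 in total. Its 83% power for a difference of 0.4 with 65 per arm comes without an SD. Taking SD = 1 and correlation 0.5, a normal approximation gives 79.8% with the stated three time points and 82.2% with four. I borrow 65 per arm, 0.4 and 0.5 below only as a scale.

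**4. Illustration for H4.** Assumptions: 65 evaluable per arm, SD 1 at each visit, constant effect 0.4 SD, correlation r between visits, two-sided 5% t-test, equal visit weights, no design effect for treatment groups.

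- Month 1: noncentrality = 0.4 × √(65/2) = 2.28, power 62%.
- Mean of three visits: SD = √((1 + 2r)/3). At r = 0.5 this is 0.816, the standardised effect is 0.4/0.816 = 0.490, and power is 79%.
- Range: r = 0.3 gives SD 0.730 and power 87%; r = 0.7 gives SD 0.894 and power 72%.
- Disagreement on significance (40,000 simulated trials): 22% at r = 0.5 (28% at 0.3, 15% at 0.7). At r = 0.5, about 20% are significant only on the average and about 2% only at month 1.

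**5. Sensitivity to time course.** Take six monthly values with mean effect 0.4 and r = 0.5. Power for the six-month mean is 84% (SD = √(3.5/6) = 0.764). If the effect rises linearly, the month-1 effect is 0.4/3.5 = 0.114, with power 10%. If it fades linearly, the month-1 effect is 6 × 0.114 = 0.686, with power 97%, and the two tests disagree in about 14% of trials. The documents support neither shape.

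**The case against.** The strongest reply is that the plan has no formal decision rule for H4. C12d opens with the trajectory GLMM over all visits, the visit contrasts follow as effect estimates, and Section 6 repeats the trajectory analysis without naming a primary time point. This stands against one reading: a reader might infer that H4 is formally decided at month 1, but that rests on a label alone. It does not remove the mismatch. Either the label governs and points to a different quantity, or nothing governs and H4 has no stated deciding contrast.

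Three other stronger readings are tempting and not supported:

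- *The later work data are discarded.* They are not. The GLMM uses every visit, and months 3 and 6 are compared. The label only ranks the results.
- *Work cannot build up by month 1.* Nothing in the documents says so. The outcome includes volunteering, and GMI Session 4 directly targets productive work and structured activity.
- *Month 1 costs a large amount of power.* This depends on an assumed build-up. If the effect fades, month 1 has the higher power.

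It is also fair to say that the aims never use the word total, and that their phrase could mean the period in which days are measured. Even so, a quantity measured over that period is not a month-1 difference. The day/percent discrepancy alone is minor; what remains of it is the unstated offset. Finally, H4 is secondary and unpowered, and the month-1 rule covers every outcome. That limits the weight of the point, but H4 is the one hypothesis whose own wording fixes a six-month window.

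**Conclusion.** The inconsistency is real and rests on current text: two units, a model without a stated offset, and a labelled primary time point covering about one sixth of the window in the hypothesis. As written, the leading H4 contrast does not answer H4, and no other stated contrast does. This should be corrected before analysis. It changes no sample size and no primary outcome.

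The figures of about 62% against 79% power, with 22% disagreement, show only that the choice of contrast can matter. They rest on a constant effect, inputs borrowed from the substance-use calculation, and a Gaussian approximation to an outcome the plan treats as a count, possibly with excess zeros. The true direction and size of any gain are unknown because the time course is unknown. The definitional mismatch depends on none of these assumptions.

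**What to change.** In C12 and C12d:

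- Exempt H4 from the month-1 rule.
- Name as its main contrast the GMI-CT difference in work/volunteer days over follow-up to month 6, estimated from the count GLMM across the month 1, 3 and 6 PWAC records with log(calendar days covered) as offset.
- State how visits are combined, for example weighted by the length of interval each record represents, and how the log-link result is converted to days.
- Report month-specific contrasts and monthly percentages as supportive.

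Use the same definition in the Specific Aims, C12, C12c, C12d and Section 6. Table 5 numbers productive work as H2 and quality of life as H4; align that numbering too.

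State the PWAC look-back. If each record covers the time since the last visit, the contrast is close to a literal count of days. If it does not, the offset makes it a rate over observed days, and the text should say so.

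The cost is mainly wording, since the calendar is already collected at these visits. Lengthening the look-back, if wanted, would also change data collection. The H4 result would wait for month 6 and be more exposed to dropout than a month-1 comparison.

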### **B. BACKGROUND/SIGNIFICANCE**

**B1. Supportive housing for homeless Veterans is a national priority within VA.** Veterans account for 13% (tens of thousands) of all homeless adults at any given point in time and suffer unmet need for health/social services and high mortality. Combining initiatives, \$941 million was proposed for FY 2014 for VA homeless programs. *Two cardinal VA housing programs collectively referred to as ‘VA housing’, are: Housing and Urban Development-Veterans Affairs Supported Housing (HUD-VASH, n= 56,850 slots) and Grant & Per Diem (GPD, n= 15,500 slots as of August, 2013).* HUD-VASH combines rental assistance for homeless Veterans with case management; *whereas GPD awards grants to community agencies for transitional housing programs that help Veterans regain social function and re-enter work and housing. Together, VA housing programs support over 150,000 homeless Veterans, reflecting massive expansion in the last 4 years.*

**B2. Substance abuse is common among homeless Veterans.** Over 60% of Veterans are admitted into VA housing with a SUD. About 50% have both alcohol and drug use disorders. Some clients with severe alcohol dependence reduce drinking once housed, although most comparative studies have not found an overall beneficial impact of housing on the SUD itself. *Despite a major expansion in clinical services, substance abuse overdose is the leading cause of death among formerly and currently homeless adults.* Substance use is a *risk factor* for recidivism to homelessness and having a co-existing psychiatric disorder (e.g., PTSD) increases the risk of loss of housing by 85 percent. The potential success of supportive housing for homeless Veterans in VA housing depends on effective treatment approaches that are respectful and impart autonomy.

**B3. Veterans in VA housing are at high risk of continued impairment in health and social functioning.** In one national study of 29,143 Veterans in VA housing, participants with a SUD reported greater psychopathology, engaged in more substance use over time, and showed more problems with alcohol and drugs at 6 months compared to VA housing participants without a substance use problem, indicating that active substance use impedes quality of life and functioning. A significant number of Veterans in VA housing also report continued social isolation and show limited improvement in social integration despite being housed. **Supportive housing is not adequate by itself to address the mental health, psychosocial, and substance abuse treatment needs of Veterans in VA housing.**

**B4. Housing First, adopted as VA’s official approach to VA housing services, necessitates additional “wraparound” treatment services.** Housing First (HF) is an evidence-based approach to supportive housing that emphasizes provision of subsidized housing as well as recovery support and case management services to the most vulnerable Veterans without preconditions of sobriety or involvement in treatment. HF combines rapid housing with “wraparound” services, thereby addressing mental health and addiction treatment needs. Pathways to Housing is an evidence-based HF model that uses Assertive Community Treatment (ACT) teams. ACT teams have been deployed on a pilot basis in 14 VA Medical Centers, and are well positioned to have a key role. However, alternatives to ACT also are needed because they are costly, not all clients require them, and case managers handling ratios of 25-36 clients per manager remains the default method of assuring clinical

support. VA leadership mandates that support services should be “wrapped around the Veteran” to advance housing stabilization, quality of life, health outcomes, and long-lasting strides to recovery (Electronic communication sent October 15th, 2012 to all VHA VISN Directors on behalf of [name]).

**B5. The ‘wraparound’ treatment mandate highlights a potential void in optimizing SUD support in both types of VA housing.** *With HUD-VASH, where harm reduction is a guiding philosophy and case managers are focused on logistics of housing, there is need for addiction interventions that respect client priorities, are relatively non-directive (consonant with harm reduction) and not staff-intensive. In GPD, current provision of SUD supportive care varies in relation to client needs and by program site. National leaders have expressed strong interest in diverse, non-resource intensive recovery support mechanisms (Personal Communication; GPD National Director [name], 11/7/2013). Given the uneven execution of SUD treatment support in both VA housing modes, our study offers a potentially valuable remedy to a pressing system need.*

**B6. Addiction recovery supports for VA housing are required that operate on lean staffing models fully aligned with the philosophic emphasis of HF on consumer autonomy.** There remains a need for SUD programs that are shorter in duration, efficient to deploy, easily layered onto existing VA housing services, require minimal staff to operate, and provide several paths of SUD assistance (e.g., lowered substance use, dual diagnosis recovery awareness, higher treatment engagement). **Our proposed study addresses this gap in VA services and will investigate the effectiveness, implementation, and process of an adaptation of motivational interviewing (MI) in a group format (i.e., GMI) that is provided in VA housing for Veterans with SUDs and comorbid psychiatric disorders.** GMI is based on MI; the latter possesses a significant evidence base for addictive disorders and has well-established effectiveness in real world settings.

**B7. Group motivational interviewing (GMI), an understudied intervention, may be a feasible/practical mode of treatment delivery and is consonant with HF.** For years an effective group-based MI intervention for addictive disorders eluded investigators due to difficulties with translating key individual MI therapeutic components into a group format. Only a few controlled trials examined MI in groups and few clinicians are trained to provide MI in groups. As a consequence, MI is underutilized in practice despite its high potential to benefit dually diagnosed Veterans. [name] developed and pilot tested a 4-session manualized GMI intervention addressing these translation issues prior to her CDA-2, (see Research Plan outlining innovative GMI components), referred to as ‘Group Motivational Interviewing Treatment (GMI) for Individuals with Psychiatric and Comorbid Substance Use Problems’; also see treatment manual in Appendix). GMI is designed to foster important aspects of group therapy that offers advantages over individual treatment (i.e. peer support, group cohesiveness), opportunities to share information, role modeling, peer feedback, altruism, and instillation of hope, while remaining consistent with the MI principles. To date, only 2 controlled trials evaluated GMI for substance use and treatment engagement among dually diagnosed patients with promising results (see section C). GMI is a useful intervention that is easily layered onto existing treatment for enhancing treatment engagement and reducing substance use among dually diagnosed Veterans. Given the recent adoption of HF as an approach in VA housing for homeless Veterans with SUDs, the delivery of MI for these individuals comes at a critical time for promoting their stabilization and quality of life.

**B8. GMI concept description.** In GMI, group members are introduced to a ‘GMI culture’ (Phase I) involving MI consistent group norms for maintaining MI Spirit (e.g., avoid giving unsolicited advice). Second, the MI processes and core MI microskills are facilitated through a set of group therapy dynamics (Phase II) that, according to Irvin Yalom^12, are most effective in group therapy. It is the *interplay between MI and these central organizing group dynamics that is the essence of GMI*. The schematic below shows the two primary GMI phases and the 10 dynamic aspects of group therapy and associated GMI strategies to accomplish the dynamic aspect: (See ‘Project Logic Model’ in Table 5 for Summative Intervention Impacts and Outcomes)

| Phase I: GMI Normative Culture (group norms, MI therapist modeling, group MI practice)                            |  |  |  |   |
|--|--|--|--|---|
| Phase II: Yalom’s (1995) Group Dynamics and Associated GMI Activities   |  |  |  |   |
| Altruism
-Brainstorming treatment obstacles/solutions
- Dual diagnosis recovery : Three legged stool | Group cohesiveness
-Normalizing ambivalence/emotions
-Brainstorming treatment obstacles/solutions | Universality
-A Hard Choice: Finding Your own pace
-Values exploration
-Interacting relationship between substance use and mental health | Interpersonal Learning
-Personal strengths
-Values clarification
-Proactive behavior: good mental health/positive outcomes | Guidance
-Establishing GMI culture
-Brainstorming treatment obstacles/solutions
-Decisional balance
-Personal feedback |

|  |   |   |  |  |
|--|---|---|--|--|
|  |   | -Therapist four open-ended questions  | -Brainstorming treatment obstacles/solutions   | -Proactive behavior: good mental health/positive outcomes  |
| Identification
-Proactive behavior: good mental health/positive outcomes | Catharsis
-Normalizing ambivalence/emotions
-Therapist four open-ended questions
-Personalized feedback | Self-Understanding
-Values Clarification
-Decisional Balance
-Dual Diagnosis recovery
-Personalized feedback
-Importance/confidence | Instillation of Hope
-Normalizing ambivalence
-Personal strengths
-Importance/confidence
-Personalized feedback
-Brainstorming treatment obstacles/solutions | Existential Factors
-Dual diagnosis recovery: 3-legged stool (staying sober, taking meds, attending treatment)
-Values exploration
-Personal strengths |

**B9. Significance to Veterans:** Homeless Veterans with SUDs represent one of the largest and most chronic groups of psychiatric patients treated in the VA Healthcare System. With the ongoing execution of VA’s “Plan to End Veteran Homelessness,” Veterans entering housing require interventions that can be feasibly implemented with minimal reorganization of existing services. GMI is based on MI, an empirically valid treatment that aligns with Veteran-centered recovery models including Harm Reduction and more traditional treatment philosophies. The investment in GMI for VA housing may be minimal as it requires only a few staff to operate in relatively short time (e.g., 4 sessions, 90-min each) with modest (20 hours) staff training. It can be layered onto existing services with little interruption or reorganization of staff, and it has potential to be offered to larger numbers of Veterans with SUDs in VA housing who would otherwise not receive this intervention.

